#### 5.12.5. Physical and Neurological Examinations

At Screening a complete physical (evaluation of the skin, head, eyes, ears/nose/throat, neck, thyroid, lungs, heart, lymph nodes, abdomen, and extremities) and neurological examination (evaluation of appearance and behavior, including observation for tremor and abnormal movements, and an evaluation of speech, cranial nerves (2-12), motor (muscle strength), muscle tone, sensory abnormalities, coordination, gait, and tendon reflexes) was performed. These results will be summarized by body system (by treatment group and overall).

Results from the targeted examinations performed at subsequent visits (including examinations after the first dose of study drug up to 14 days after the last dose date) will be summarized by presenting the number and percentage of subjects within each category by visit and by body system/parameter evaluated. For the physical examination, each body system is assessed as Normal or Abnormal. For the neurological examination, each body system is assessed as Normal, Abnormal or Absent.

All physical and neurological examination findings will be presented in subject data listings.

Sponsor:	TauRx Therapeutics Ltd.		
Protocol:	TRx-237-039		
Document Version No.:	3.0	Document Date:	07-JUN-2023

#### 5.12.6. Ophthalmological Examination

Slit lamp ophthalmological examination of subjects with lens implants will be performed at Screening and at the Week 52 visit (or upon early termination), to assess whether the lens has been discolored during the trial. In addition, the slit lamp examination could also be performed if a subject had cataract surgery / lens implantation at any point during his or her study participation (as soon as possible after the surgery), as well as in response to visual complaints if suggestive of lens discoloration.

The following information will be used to identify subjects with lens implant:

- eCRF Medical History: *Does the subject have intraocular lens implants?* = Yes
- eCRF Medical History: Coded PT term = Cataract or Cataract operation
- eCRF Procedures / Therapies: *Was this procedure an intraocular lens implant?* = Yes

Results from the examination will be summarized by treatment phase (pre-treatment, double-blind treatment phase, and open-label treatment phase), presenting the number of subjects with lens implant, the number of subjects with lens implant and at least one examination during each treatment phase, and the number and percentage of subjects within lens discoloration by treatment phase, and treatment group.

A subject data listing will display the date of the ophthalmological examination, whether the lens was discolored, and any additional details.

Sponsor:	TauRx Therapeutics Ltd.		
Protocol:	TRx-237-039		
Document Version No.:	3.0	Document Date:	07-JUN-2023

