- f Targeted examinations will be performed by a medical assessor (M) pre-dose and approximately 3 hours after administration of the first dose of study drug (Visit 2). Thereafter, targeted examinations are to be performed at each subsequent clinic visit (or upon ET). At a minimum, targeted examinations should include heart and lung auscultation and brief neurological assessment guided by any reported signs/symptoms/AEs (e.g., evaluating subjects for potential serotonin toxicity).
- g Ophthalmological examination (slit lamp) is to be performed only in those subjects with history of lens implant to evaluate discoloration of lens. The initial examination will be performed prior to the first dose of study drug (during the screening procedures or as part of the baseline assessments); performance of this examination is not restricted to the 2 to 3 days before the first dose of study drug. The final evaluation (EOT/ET) should be done after completion of the efficacy assessments.
- h At each identified time point, blood samples will be obtained for chemistry and hematology panels; results are to be reviewed by a medical assessor (M). Testing is also to be performed as needed to follow-up on an AE.
- i Serum pregnancy testing is to be performed at each identified time point in women of childbearing potential only.
- j Within 1 hour prior to dosing on Day 1, blood pressure and pulse will be measured with subjects in a seated position (for at least 5 minutes). The post-dose measurement on Day 1 is to be made approximately 2 hours post-dose (after the 1-2 hour PK sample is taken). Body weight will be measured at each visit (pre-dose at Visit 2).
- k Compliance with study drug will be assessed by counting returned tablets (see Section 12.6).

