## **16.11 Guidance for the Handling of Adverse Events of Special Interest and Selected Test Abnormalities**

The pre-specified AESIs in this study are hemolytic anemia and lens discoloration. Guidelines for the monitoring and management of the AESIs are given below along with selected test abnormalities. Clinical circumstances requiring additional evaluation of a subject and/or potential interruption or discontinuation of study drug are presented.

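### SAP 5.12.6 lets a coded history of Cataract, with no evidence of surgery, count as a lens implant, which overstates the implant group and understates examination coverage

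*SAP*

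**What the plan says.** Protocol 16.11 names two adverse events of special interest: "The pre-specified AESIs in this study are hemolytic anemia and lens discoloration". The protocol ties the scheduled eye examination to implant status. Table 10-2, footnote g, states: "Ophthalmological examination (slit lamp) is to be performed only in those subjects with history of lens implant to evaluate discoloration of lens". Sections 15.4 and 16.11.2 say the same, and add unscheduled examinations after on-study cataract surgery or lens implantation and for visual complaints that suggest discoloration.

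SAP 5.12.6 builds the corresponding analysis set. It introduces the rule with "The following information will be used to identify subjects with lens implant" and gives three bullets:

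- a Yes to the direct question on implants on the Medical History page;
- "eCRF Medical History: Coded PT term = Cataract or Cataract operation";
- a Yes on the Procedures page to the question whether a recorded procedure placed an implant.

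The summary is then described as "presenting the number of subjects with lens implant, the number of subjects with lens implant and at least one examination during each treatment phase", followed by the number and percentage with discoloration by phase and treatment group. No denominator is given for that percentage. SAP 6.13.6 repeats the summary for the Safety-OL population.

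**The concern.** The second bullet puts a diagnosis beside a procedure. Cataract operation is evidence of surgery. Cataract alone describes a lens that may never have been operated on. The SAP lists the two terms separately and asks for no further evidence when only the diagnosis is present.

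The set analysed is therefore wider than the set the protocol sends for scheduled examination. Subjects who have a cataract history but no implant enter the first count in the summary and mostly cannot enter the second, because no examination was scheduled for them. A reader comparing the two counts would see a shortfall in safety examinations that the protocol never asked for. This matters because the summary is the only place where the SAP relates lens discoloration to the implant group.

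**Working it through.** **Are the bullets alternatives?** The SAP prints neither AND nor OR. The bullets come from a history question, a coded history term and a procedures-page question. Requiring all three would demand both a history entry and a procedures-page implant record from the same subject, which would leave almost nobody. Reading them as alternatives is the only workable interpretation. On that reading, a No to the direct implant question does not keep out a subject who has a Cataract term. The SAP does not say how conflicting sources are to be resolved.

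**Who is examined?** Protocol 15.1 has lens implantation history recorded in medical history. Protocol 10.5.2.3 bars sites without a qualified examiner from screening subjects who have an implant history, so implant status has to be known at screening. A cataract-only subject reaches an examination only through on-study surgery or suggestive visual complaints (16.11.2). On-study implants are already caught by the third bullet, so the Cataract term is not needed for them.

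**Effect on the counts.** The documents state no figure on this point, so there is nothing of the plan's to reproduce. Let r be the number of cataract-only subjects per true implant subject.

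- Reported number with implant = true number × (1 + r).
- Reported coverage = true coverage ÷ (1 + r), if only true implant subjects are examined.
- Reported discoloration percentage = true percentage ÷ (1 + r), if the denominator is everyone classed as having an implant.

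The values of r, the 90% coverage and the 10% discoloration rate below are all assumptions chosen for illustration.

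| r | Implant count multiplied by | 90% coverage shown as | 10% discoloration shown as (denominator: all classed as implant) |
|---|---|---|---|
| 0 | 1.00 | 90.0% | 10.0% |
| 0.10 | 1.10 | 81.8% | 9.1% |
| 0.25 | 1.25 | 72.0% | 8.0% |
| 0.50 | 1.50 | 60.0% | 6.7% |
| 1.00 | 2.00 | 45.0% | 5.0% |

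For example, at r = 0.50, 90 ÷ 1.5 = 60.0 and 10 ÷ 1.5 = 6.7.

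**Effect under the other denominator.** If the percentage is taken over implant subjects with at least one examination in the phase, the last column changes little, because scheduled examinations are confined to true implant subjects. The only leakage is from cataract-only subjects examined for visual complaints.

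**Effect on the special-interest event tables.** SAP 5.12.2 and 6.13.2 tabulate these events from a list of identified events supplied to the programmers, within the safety populations set in 5.12 and 6.13. The implant rule does not enter either table.

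**The case against.** The strongest defence has four parts.

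1. **Nothing decisive depends on this summary.** It is descriptive, adverse event incidence is not formally tested, and every examination result is listed by subject, so no finding is lost. The rule uses history data, so any misclassification should be similar across randomised arms. This stands, and it limits the importance of the point. It does not make the implant count correct.

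2. **The rate may not be diluted at all.** The SAP prints the number of examined implant subjects just before the percentage, and that is the natural denominator. This also stands. A reader might infer that the rate of a special-interest event is understated in every arm. The documents do not support that: the event tables do not use the implant rule, and dilution of the percentage in 5.12.6 depends on a denominator the SAP does not state.

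3. **A wider net may be deliberate.** The Version 4.0 entry in the protocol's summary of changes (28.4.4) lists lens implantation history among the baseline characteristics to be collected, and SAP 1.3 bases safety on all randomised subjects. The direct question may therefore not have been asked uniformly of the earliest subjects. This is a good reason to keep Cataract operation as a fallback, and a reason not to rely on the two direct fields alone. It does not justify classing an unoperated cataract as an implant. It supports a query instead.

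4. **The alternative reading of the bullets is inferred.** That is correct, but no other reading gives a usable set.

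**Conclusion.** The definition is wrong as written. If even one subject has a Cataract term and no implant, the number of subjects with a lens implant is too high. Apparent examination coverage is then too low unless that subject happens to have been examined. Both hold in 5.12.6 and in 6.13.6.

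The size cannot be determined. Eligibility extends to any age below 90 (Protocol 11.1), which makes such subjects plausible, but the documents give no cataract prevalence and the effect could be trivial. It would be tempting to conclude that the number affected must be large, or to quote a discoloration rate cut from 10% to between 5.0% and 6.7%. Those figures need r between 0.50 and 1.00 and the all-implant denominator, and neither is established.

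The conclusion rests on two things: that the three bullets are alternatives, and that a coded diagnosis of cataract does not by itself establish surgery. The error is confined to one descriptive safety summary and its open-label repeat. The special-interest event tables and the efficacy conclusions are not touched. The correction is cheap and should be made.

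**What to change.** In SAP 5.12.6:

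- Remove Cataract as a stand-alone criterion. Where it is the only indication, raise a data query on implant status.
- Class a subject as having an implant if the eCRF implant question is Yes, or the Procedures implant field is Yes, or the coded history term is Cataract operation (as a fallback). State that any one of these is enough.
- State that the denominator of the discoloration percentage is subjects with a lens implant and at least one examination in that phase.

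Apply the same wording to 6.13.6.

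The cost is a few lines of SAP text, one changed derivation, and queries for the subjects whose only indication is the Cataract term. No new assessment is needed. The double-blind snapshot has already been taken (SAP 10), but SAP 1.6 allows the double-blind analysis to be re-run on the final locked data. The corrected summary can be produced then and recorded as a change to the planned analyses.

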## **6. STATISTICAL ANALYSIS OF OPEN-LABEL TREATMENT PHASE**

### **6.1. Introduction**

The rationale of a delayed-start design is that, when the active drug has a purely symptomatic effect and has no effect on neuropathologic process, a delay in administration should have no lasting effect on subjects (null hypothesis). An effect that slows the progression of disease by modifying the underlying biological pathology, rather than only attenuating symptoms, would be evident if late starters fail to “catch up” to early starters. Demonstrating a disease-modifying effect would imply a sustained benefit of starting such drugs early. Throughout (that is, both the controlled and delayed-start phases), all subjects and study personnel on-site are blinded to each subject’s randomization to the early-start or late-start treatment group (HMTM treatment history).

Only subjects completing the 52-week double-blind treatment phase on- or off-treatment are eligible to enter the open-label treatment phase. This includes subjects, that have been randomized under a protocol version before version 5 and includes subjects who re-consented on a protocol version 5+ after the randomization and who completed the 52-week double-blind treatment phase. Subjects who have been off-treatment at Week 52 (TOTOS) stay off-treatment and do not receive any open-label treatment phase study drug.

### **6.2. Open-Label Treatment Phase Definitions**

Based on the HMTM treatment history during the double-blind treatment phase “late” starters are defined as subjects originally randomized to control, and “early” starters are defined as subjects originally randomized to HMTM 16 mg/day or HMTM 8 mg/day. The last available assessment – for the scales: the last available (upscaled) value – prior to or on the same day of the start of the open-label treatment (Visit 7, Week 52) will serve as the Baseline assessment of the open-label treatment phase (Baseline-OL). A delayed performed Week 52 MRI assessment will be eligible for the Baseline-OL assessment if it has been done within 14 days after starting the open-label treatment phase.

The treatment group of subjects originally randomized to control will be labeled as “MTC 8 mg/week”.

### **6.3. Summary Statistics**

Summary tables and most of the efficacy tables will be presented by the original randomized treatment group from the double-blind treatment phase and will have the following labels:

- “MTC 8 mg/week -> HMTM 16 mg”,
- “HMTM 8 mg -> HMTM 16 mg”,

Sponsor:	TauRx Therapeutics Ltd.		
Protocol:	TRx-237-039		
Document Version No.:	3.0	Document Date:	07-JUN-2023

---

- “HMTM 16 mg -> HMTM 16 mg”, and
- “HMTM Pooled -> HMTM 16 mg”.

The “MTC 8 mg/week -> HMTM 16 mg” group presents the “late starters” and the “HMTM Pooled -> HMTM 16 mg” group presents the “early starters” (i.e., HMTM 8 mg and HMTM 16 mg). An explanatory footnote will be added to explain this. A total column, combining the early and late starters, will be presented as needed.

Summary statistics are described in more details in the post hoc efficacy Section 6.12.

Subject data listings conducted during the double-blind treatment phase will be re-run including the open-label treatment phase data, if open-label treatment phase data is available. If appropriate, a flag for open-label treatment phase data will be added and the open-label treatment phase study day will be presented as well (for subjects who have entered the open-label treatment phase). The treatment group labels for subjects participating in the open-label treatment phase as well will be changed to: “MTC 8 mg/week -> HMTM 16 mg”, “HMTM 8 mg -> HMTM 16 mg”, and “HMTM 16 mg -> HMTM 16 mg”; whereas the treatment group labels for subjects not participating in the open-label treatment phase stay unchanged: “Placebo Only”, “MTC 8 mg/week”, “HMTM 8 mg”, and “HMTM 16 mg”.

The summaries of assessments affected by COVID-19 (see Section 4.8), which are presented by study visit for the ITT population, will be extended by the open-label treatment phase study visits.

#### 6.4. Sample Size Justification

With about 400 subjects randomized to control or HMTM 16 mg/day under protocol version 5.0 and above, which is the primary treatment group comparison in the double-blind treatment phase, an estimated 160 to 170 subjects per arm will enter the open-label, delayed-start phase assuming the dropout rates from Section 5.3. Assuming a further 10% drop out in the delayed-start phase, the key secondary analysis to demonstrate disease modification by comparing early to late starters with a noninferiority margin of -2 ADAS-cog11 units has approximately 80% power.

#### 6.5. Protocol Deviations

The protocol deviations file, which was finalized for the double-blind treatment phase analysis prior to the unblinding of the double-blind treatment phase will be updated prior to the database lock of the open-label treatment phase.

This file will include a description of the protocol deviation, will provide the information regarding previous classification (minor/major), and will provide the classification done by the Sponsor into important/non-important.

The level of detail and information will provide full traceability.

---

Sponsor:	TauRx Therapeutics Ltd.		
Protocol:	TRx-237-039		
Document Version No.:	3.0	Document Date:	07-JUN-2023

Based on the ITTv5-OL and ITT-OL populations, summaries by categorization (important/non-important) and type (or code) will be provided. This will be done pooled and separately for COVID-19- and non-COVID-19-related protocol deviations. Also, one version will count all protocol deviations and one version will count only the overall unique deviations (when one deviation is resulting in subsequent ones).

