### 17.3 Analysis Populations

The following subject populations will be used for the statistical analyses; all definitions reply on the treatment period in the double-blind phase excluding open-label assessments (population definitions will be used for the delayed-start analyses without any modifications):

- Intent-to-Treat (ITT) population will include all randomized subjects. Three subsets are defined as follows:
  - The Efficacy Modified Intent-to-Treat (E-MITT) population will include all randomized subjects who take at least one dose of the study drug and have a baseline and at least one valid post-baseline efficacy assessment in the treatment period (prior to any potential follow-up assessment).
  - An MRI Imaging Modified Intent-to-Treat (MI-MITT) population will include all randomized subjects who took at least one dose of study drug and have at least one valid baseline and at least one valid post-baseline volumetric MRI.
  - The Imaging Modified Intent-to-Treat population (PI-MITT) for F-FDG-PET will include all randomized subjects with screening CDR 0.5 who took at least one dose of study drug and have a baseline and a valid post-baseline SUVR assessment.
- The Per Protocol (PP) population will include all subjects who are in the E-MITT and MI-MITT populations and who do not have any PP exclusionary protocol deviations or intercurrent medical events that could confound the interpretations. PP exclusionary deviations, irrespective of their classification as minor/major, and intercurrent medical events will be determined prior to treatment unblinding.
- The Safety population will include all randomized subjects who take at least one dose of study drug.

Due to the introduction of MTC spiking in the placebo arm with Protocol Version 5.0, the respective MITT populations will be restricted to subjects randomized to Protocol Versions 5.0 and above for the primary and key secondary analyses as per the SAP. The full MITT populations will be analyzed for these as a sensitivity analysis. Details will be provided in the SAP. For the ITT, respective restrictions will be applied as part of the first step in the EMA analysis (see Section 17.4.3).

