#### **17.4.6 Open-Label, Delayed-Start Analysis**

“Late” starters, *i.e.*, subjects originally randomized to placebo, will be compared to “early” starters, *i.e.*, those originally randomized to LMTM 16 mg/day or 8 mg/day (pooled, and individually for both groups as a sensitivity analysis). The last assessment prior to start of open-label treatment (pre-dose at Visit 7) will serve as the baseline assessment for these comparisons. The analyses will be based on a similar linear mixed model for repeated measures as outlined for the FDA/EMA primary analysis (see model specification in Sections 17.4.2 and 17.4.3) with the aim to investigate whether there is a difference in change in primary and MRI imaging endpoints dependent on LMTM treatment history (certain covariates in the model might be dropped if the model does not converge; see SAP for details).

The comparison will be implemented through a non-inferiority test. The non-inferiority margin for the primary endpoint of ADAS-cog11 will be 2 units, motivated by the fact that these 2 units are small compared to the estimated treatment effect of > 5 units (~40% of this effect size). Margins for other endpoints which are exploratory to support a disease modifying argument will be defined in the SAP.

The results will also be presented with the Visit 2 Baseline as baseline, and treatment visits Week 26 and Week 52 in the open-label, delayed-start phase as Week 78 and Week 104.

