**Pharmacokinetic (PK) Population:** all subjects who were administered at least one dose of study drug and have at least one analyzable post-dose PK sample.

Sponsor:	TauRx Therapeutics Ltd.		
Protocol:	TRx-237-039		
Document Version No.:	3.0	Document Date:	07-JUN-2023

The analysis of estimands is based on the ITT population. For the FDA, the modified endpoint specific ITT populations (MITTs) will be analyzed. The Safety population is the primary population for the analysis of safety endpoints.

Two population trackers will be generated and will be provided to Cytel for the use in the analyses. The first as a result of the double-blind treatment phase BDRM, and the second as a result of the open-label treatment phase Data Review Meeting (DRM). These trackers will specify if subjects are included or need to be excluded from certain populations (e.g., TOTOS, PP, PP-OL). The population tracker from the BDRM will also specify if dropouts are potentially related to treatment.

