#### 6.10. Secondary Efficacy Endpoint Analysis

The goal of the open-label phase is to demonstrate disease modification by comparing the ADAS-cog11 change from Baseline-OL at Week 104 between early and later starters using a non-inferiority margin. According to the study protocol the non-inferiority margin will be set to 2 units, based on the estimated treatment effect of  $5.2 \pm 1.3$  (mean  $\pm$  standard error) units from a pooled analysis of the studies TRx-237-005 / TRx-237-015.

This non-inferiority margin, and the thresholds mentioned in Section 6.11, have been selected based on the results of the two previous phase 3 studies TRx-237-005, and TRx-237-015. It was planned to change the non-inferiority margin to 50% of the observed 52 treatment effect, should the decline and treatment effect for this study, seen after topline and full analysis of the double-blind treatment phase, deviate strongly from the expectations based on the TRx-237-005/TRx-237-015 results. With the knowledge of the double-blind treatment phase results, the non-inferiority margin will be as selected, based on the two previous phase 3 studies TRx-237-005, and TRx-237-015.

Efficacy analyses will be conducted using the PPv5-OL population (see Section 3.1.2) with no imputation of missing values. Upscaling for the scales will be performed. The ITTv5-OL population will be analyzed as a supplementary analysis and will include only those subjects with at least one post-Baseline-OL value.

The key secondary endpoint is the Baseline-OL adjusted decline in ADAS-cog11 from Baseline-OL at Week 104. Repeated measures on this endpoint scheduled at Week 78, and Week 104 will be treated using a mixed effects model. Suppose  $\mu_{\text{early}}$  and  $\mu_{\text{late}}$  are the corresponding means of decline at Week 104 for the early and late starters, then the null and alternative hypothesis can be written as:

$$H_0: \mu_{\text{early}} - \mu_{\text{late}} \geq 2; \text{ versus}$$

Sponsor:	TauRx Therapeutics Ltd.		
Protocol:	TRx-237-039		
Document Version No.:	3.0	Document Date:	07-JUN-2023

$H_1: \mu_{\text{early}} - \mu_{\text{late}} < 2$ .

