### 10. CHANGES TO PLANNED ANALYSES

The exploratory efficacy F-FDG-PET parameters inferior temporal gyrus and angular gyrus will not be analyzed, since these are included in the lateral temporal cortex and parietal cortex region of interests, respectively.

The exploratory Bayesian analysis, accounting for and using historic data more generally such as placebo decline or treatment effects as priors to inform the analyses of this study, will not be performed.

After the data snapshot (28-APR-2022), the SAP v2.0 signature and the partial study team members unblinding to perform the analysis of the double-blind treatment phase, the version 2.0 of the SAP has been updated to a version 3.0 with added analyses.

Sponsor:	TauRx Therapeutics Ltd.		
Protocol:	TRx-237-039		
Document Version No.:	3.0	Document Date:	07-JUN-2023

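### The delayed-start key secondary is decided on a per-protocol set (PPv5-OL) whose open-label exclusions need not be settled before unblinding, contrary to Protocol 17.3

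*SAP*

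**What the plan says.** **Protocol.** Section 17.3 builds every analysis population on the double-blind phase and then states that the "population definitions will be used for the delayed-start analyses without any modifications". It also requires the deviations that exclude a subject from the Per Protocol set to be settled before treatment is unblinded. Section 17.4.6 analyses delayed start with a model similar to that "as outlined for the FDA/EMA primary analysis"; those analyses use E-MITT and ITT.

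**SAP.** Section 3.1.2 creates a new set, PP-OL: randomized subjects who took open-label drug and had no important open-label deviation. Section 6.10 then says "Efficacy analyses will be conducted using the PPv5-OL population (see Section 3.1.2) with no imputation of missing values", and "The ITTv5-OL population will be analyzed as a supplementary analysis". The sponsor, or its designee, decides which deviations are important (Sections 3.2 and 6.5).

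For the double-blind phase the deviation file had to be final before unblinding, and the population tracker came from a Blinded Data Review Meeting. For the open-label phase the file "will be updated prior to the database lock of the open-label treatment phase". Section 3.1.1 describes two trackers, "the second as a result of the open-label treatment phase Data Review Meeting (DRM"; the word blinded does not appear there. Section 10 records that SAP v3.0 followed the 28-APR-2022 snapshot and "the partial study team members unblinding to perform the analysis of the double-blind treatment phase". It does not list the change of population.

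**The concern.** The delayed-start test carries the disease-modification claim. When one set decides that test, and membership depends on a sponsor judgement that may be made after treatment codes are available to part of the team, the plan has to show that the judgement is blind to arm. The double-blind rules do this and the open-label rules do not.

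A non-inferiority result is sensitive to who is left out. Removing a few early starters with poor outcomes moves the estimate towards success, and the ITT-type set that would reveal this has no part in the success decision.

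**Working it through.** **1. The two sets of rules side by side**

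| Item | Protocol 17.3 / double-blind SAP | Open-label SAP |
|---|---|---|
| Populations | Double-blind definitions, carried over unchanged | New PP-OL set (3.1.2); PPv5-OL decides (6.10) |
| Ground for per-protocol exclusion | Important deviation that the blinded meeting also judges exclusionary (SAP 3.1.1) | Any important open-label deviation (SAP 3.1.2) |
| When settled | Before unblinding (Protocol 17.3, SAP 3.2) | Before open-label database lock (SAP 6.5) |
| Meeting | Blinded Data Review Meeting | Data Review Meeting |

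Two other PPv5-OL conditions, having taken open-label drug (SAP 3.1.2) and having a Week 52 value (SAP 2.4), are objective and not at issue.

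**2. The plan's own power figure.** SAP 6.4 states about 80% power. Inputs: margin 2 units, one-sided alpha 0.025 (SAP 6.10), SD 5.9 (SAP 5.3, given for the double-blind year and assumed here for the open-label year), true difference 0, 10% open-label dropout (SAP 6.4).

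Power = Φ(2 / (5.9 × √(2/n)) − 1.96)

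- 150 entering per arm, n = 135: standard error 0.718, power 0.795
- 160 entering, n = 144: standard error 0.695, power 0.820
- 170 entering, n = 153: standard error 0.675, power 0.843

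The stated figure reproduces at 135 to 144 per arm.

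**3. How far exclusions could move the estimate.** Early starters are 200 + 50 = 250 randomized. With 25% and then 10% dropout, 250 × 0.75 × 0.90 ≈ 169 remain, against 200 × 0.75 × 0.90 = 135 late starters. The number removed (k) and their excess decline (d) are assumptions; neither is in the documents.

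Shift in the raw early mean = k × d / (169 − k)

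- k = 2, d = 10: 20/167 = 0.12 units, 6% of the margin
- k = 5, d = 5: 25/164 = 0.15 units, 8%
- k = 5, d = 10: 50/164 = 0.30 units, 15%
- k = 9, d = 10: 90/160 = 0.56 units, 28%

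The standard error of the early-minus-late difference is 5.9 × √(1/169 + 1/135) = 0.68, so a shift of 0.30 is 0.45 of a standard error. In the 16 mg-only comparison (SAP 6.10.1, a sensitivity analysis), 5 × 10/130 = 0.38 units, 19% of the margin.

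**4. Upper bound on the error rate.** This was a simulation of 20,000 trials with normal data, SD 5.9, a true difference of exactly 2, 180 early against 144 late starters (20% then 10% dropout) and an unadjusted t test. The very worst decliners were removed from the early arm only. The one-sided error of 0.025 rises to 0.046 with 2 removed, 0.075 with 4 and 0.18 with 9. This bounds the exposure and does not predict it.

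**5. Power of the sets under the fix.** With 144 per arm, assumed per-protocol exclusions of 5%, 10% or 20% in both arms give power 0.80, 0.78 or 0.73. With early starters pooled (180 against 144) the figures are 0.84, 0.82 and 0.77, compared with 0.86 without exclusions. Power to pass both sets cannot exceed that of the weaker one.

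**The case against.** Several counter-arguments are sound.

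- **Blinding of the classifiers.** Unblinding was partial. SAP 2.7 refers to a Study Blind Maintenance Plan dated 27-OCT-2022, after the snapshot, which was not available here and may keep the classifiers blinded. Protocol 10.1 and 12.8 also withhold individual assignment from those running the open-label phase. A reader might infer that exclusions were made with treatment known. No passage says so. What stands is that the SAP contains no such safeguard for this step, and SAP 1.5, 2.7 and 6.1 word the blinding commitment in terms of subjects and on-site staff.
- **When the set was chosen.** A reader might infer that PPv5-OL was picked after the double-blind results were seen, since SAP 6.10 mentions knowledge of those results in settling the margin. SAP v1.0 and v2.0 are not available, so the choice cannot be dated.
- **Per-protocol sets in non-inferiority.** They are a usual choice, because non-adherence tends to make arms alike and so eases a non-inferiority finding in an ITT-type set. ITTv5-OL is itself selected after randomization: it needs open-label entry and a later value. So the per-protocol set is not wrong in itself, and neither set should decide alone.
- **What the protocol fixes.** It does not name one deciding set for delayed start; Section 17.4.6 refers to the model, and Section 17.3 does include a Per Protocol set. That set, however, rests on double-blind deviations settled before unblinding. PPv5-OL does not.
- **Limits on discretion.** The open-label file updates one completed before unblinding, the minor/major grade is kept beside the sponsor's grade, and deviations are tabulated on the ITT-type sets. Odd exclusions would be visible. The SAP still gives only examples of deviations, not a closed list.
- **Disclosure.** The modification history records that the open-label section was updated, but neither it nor Section 10 names the population change.

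**Conclusion.** The concern holds as a departure from the protocol's own rule and a missing safeguard. The SAP lets one discretionary set decide the key secondary, and lets membership be settled up to open-label lock, after some team members were unblinded. It does not prevent exclusions made with treatment known. Nothing in the documents shows that this happened, and nothing shows that the set was adopted after unblinding.

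The size depends on assumptions. The 0.30-unit shift supposes five exclusions, all early starters and all 10 units worse than average, with none among late starters, and it is a raw mean, whereas the planned model adjusts for the open-label baseline and the strata. That is a worst case in direction. It would matter only if the result lay near the margin. The change should be made because it costs little and the claim at stake is disease modification.

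**What to change.** - **SAP 6.10:** require the 2-unit margin to be met in both ITTv5-OL and PPv5-OL.
- **SAP 6.5:** state that open-label deviations are classified by staff blinded to randomized arm, using the deviation types fixed before unblinding where they apply, and that the population tracker is dated and frozen before any open-label efficacy output by group. If the Study Blind Maintenance Plan already ensures blinded classification, a cross-reference covers that part.
- **SAP Section 10:** list the change of population from Protocol 17.3, with the reason.

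The cost is mainly wording, since both analyses are already planned. The success criterion becomes somewhat stricter: on the equal-arm basis that reproduces the plan's figure, power to pass both sets would be slightly below the stated 80% or so. The exact joint figure depends on the exclusion rate, which the SAP does not give; heavy overlap between the sets should keep the loss small.
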